#### **Induction Period**

Up to approximately 40 subjects will be enrolled in the induction period to receive the following treatment:

- Ravaglimab 600 mg intravenous (IV) Week 0; ravaglimab 300 mg subcutaneous (SC) Weeks 2, 4, 6, 8, and 10.

Once the 30th subject completes Week 8 assessments an interim analysis will occur. This interim analysis will inform the planning of future Phase 2b and 3 studies. Enrollment into the induction period may continue until approximately 40 subjects have enrolled, or enrollment may be terminated if the study objectives are determined to have been met.

An endoscopy is required at Screening, and evaluation of endoscopic improvement will occur at Week 8. In order to explore the time-course of ravaglimab efficacy, subjects will continue through Week 12 and

will be assessed for clinical response per Partial Adapted Mayo score at Week 12. Subjects who complete the induction period and achieve clinical response per Partial Adapted Mayo score at Week 12 will be given the opportunity to continue into the maintenance period. Subjects not achieving clinical response per Partial Adapted Mayo score at Week 12 will be discontinued and have a follow-up visit (or call if a visit is not possible) 84 days from the last dose of study drug to obtain information on any new or ongoing AEs.

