## 5.6 Follow-Up After Subject Discontinuation of Study Drug or from Study Participation

---

To minimize missing data for efficacy and safety endpoints, subjects who prematurely discontinue study drug treatment should continue to be followed for all regularly scheduled visits, unless subjects have decided to discontinue the study participation entirely by withdrawal of informed consent, in which no further study procedures or study activities can be performed. Subjects should be advised on the continued scientific importance of their data even if they discontinue treatment with study drug early.

If a subject prematurely discontinues from the study/study drug, the procedures outlined for the Premature Discontinuation visit (PD visit) should be completed as soon as possible, preferably within 2 weeks. In addition, if subject is willing, an 84-day follow-up visit after the last dose of study drug may be completed to ensure all treatment-emergent AEs/serious adverse events (SAEs) have been resolved.

If a subject withdraws from study follow up or withdraws permission for the collection of their personal data, the study staff may still use available public records to obtain information about survival status only, as appropriate per local regulations.

In the event a subject withdraws consent from the clinical study, biomarker research will continue unless the subject explicitly requests analysis to be stopped. When AbbVie is informed that samples are withdrawn from research, samples will not be analyzed, no new biomarker analysis data will be collected for the withdrawn subject or added to the existing data or database(s), and the samples will be destroyed. Data generated for biomarker research before subject withdrawal of consent will remain part of the study results.

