Persistent or Significant Disability/Incapacity	An event that results in a condition that substantially interferes with the activities of daily living of a study subject. Disability is not intended to include experiences of relatively minor medical significance such as headache, nausea, vomiting, diarrhea, influenza, and accidental trauma (e.g., sprained ankle).

**Important Medical Event  
Requiring Medical or Surgical  
Intervention to Prevent  
Serious Outcome**

An important medical event that may not be immediately life-threatening or result in death or hospitalization, but based on medical judgment may jeopardize the subject and may require medical or surgical intervention to prevent any of the outcomes listed above (i.e., death of subject, life threatening, hospitalization, prolongation of hospitalization, congenital anomaly, or persistent or significant disability/incapacity). Additionally, any elective or spontaneous abortion or stillbirth is considered an important medical event. Examples of such events include allergic bronchospasm requiring intensive treatment in an emergency room or at home, blood dyscrasias or convulsions that do not result in inpatient hospitalization, or the development of drug dependency or drug abuse.

All adverse events reported from the time of study drug administration until 84 days after discontinuation of study drug administration will be collected, whether solicited or spontaneously reported by the subject. In addition, serious adverse events and protocol-related nonserious adverse events will be collected from the time the subject signs the study-specific informed consent.

AbbVie will be responsible for Suspected Unexpected Serious Adverse Reactions (SUSAR) reporting for the Investigational Medicinal Product (IMP) in accordance with global and local requirements.

Adverse events will be monitored throughout the study to identify any of special interest that may indicate a trend or risk to subjects.

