9.0 Safety Analyses

9.1 General Considerations

Safety data will be summarized for the Safety Analysis Set. Safety summaries will be presented.

There are two sets of planned safety analysis: safety analysis for the Induction Period, and long-term safety analysis.

Safety Analysis for the Induction Period

Safety analysis for the Induction Period will include reporting of adverse events (AEs), laboratory, and vital signs measurements. Frequency tables of subjects with treatment-emergent adverse events (TEAEs) by system organ class (SOC) and by preferred term (PT) as in the Medical Dictionary for Regulatory Activities (MedDRA) dictionary will be provided. All continuous laboratory parameters and vital signs variables at each visit will also be summarized. Frequency tables of subjects meeting criteria for potentially clinically significant vital sign values and for potentially clinically significant laboratory values will be provided.

Long-Term Safety Analysis

Long-term safety analysis will be performed on all cumulative safety data in Induction Period and Maintenance Period up to data cutoff date for any interim lock as deemed appropriate and final lock.

Long-term safety analyses include reporting of AE rate adjusted by cumulative exposure, descriptive summary in laboratory parameters and vital sign variables, and rate of potentially clinically significant laboratory and vital signs values.

Exposure-adjusted event rate (EAER) will be provided for long term safety analysis. For EAER calculation, the numerator will be the total number of AEs reported for the event (i.e., a subject can contribute more than one event to the numerator) and the denominator

will be the total exposure time among subjects under the treatment. The number of AEs reported (numerator), the total number of years of study drug exposure (denominator calculated as total number of days exposed to study drug (i.e., last dose date – first dose date + 84 days) for all treated subjects divided by 365.25), and the exposure-adjusted AE event rate per 100 patient-years calculated as ([numerator (number of AEs)/denominator] • 100 will be presented.

All continuous laboratory parameters and vital signs variables at each visit will be summarized.

Frequency tables and listings of subjects meeting criteria for potentially clinically significant vital sign values and for potentially clinically significant laboratory values will be provided. Missing safety data will not be imputed.

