9.2.1 Treatment-Emergent Adverse Events

Treatment-emergent AEs are defined as any AE with the onset that is on or after the first dose of study drug to the last dose date prior to cut-off date + 84 days or the cut-off date for database lock, whichever occurs first. Events where the onset date is the same as the study drug start date are assumed to be treatment emergent. All treatment-emergent AEs will be summarized overall, as well as by primary MedDRA SOC and Preferred

Term. The SOCs will be presented in alphabetical order, and the PTs will be presented in alphabetical order within each SOC.

The number and percentage of subjects experiencing treatment-emergent AEs will be summarized.

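### Protocol 5.6 makes the 84-day safety contact optional for early leavers, while the AE window and the SAP exposure denominator assume that all 84 days are observed

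*Protocol*

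**What the plan says.** **The contact.** For subjects who prematurely discontinue the study or study drug, Protocol 5.6 asks for a PD visit that "should be completed as soon as possible, preferably within 2 weeks". It then adds: "if subject is willing, an 84-day follow-up visit after the last dose of study drug may be completed". The stated purpose is to see that treatment-emergent events have resolved. No call is offered as an alternative.

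Elsewhere the contact is not conditional. Under Protocol 4.1, Week 12 non-responders are to "have a follow-up visit (or call if a visit is not possible) 84 days from the last dose of study drug", to learn of new or ongoing AEs, and maintenance completers have the same visit or call. The footnotes to both activity schedules in Appendix D, and the 84-day entry in Operations Manual 2.1, also describe a visit, or a call if a visit is not possible, with no willingness condition.

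**The window.** Protocol 6.1 says that all AEs from the start of study drug "until 84 days after discontinuation of study drug administration will be collected". Operations Manual 4.1 gives the same period and equates it to 5 half-lives.

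**The analysis.** SAP 9.2.1 runs the treatment-emergent window "to the last dose date prior to cut-off date + 84 days", or to the cut-off if that comes first. SAP 9.1 computes the exposure denominator as last dose date minus "first dose date + 84 days) for all treated subjects divided by 365.25". It sets no limit at last contact or at cut-off.

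**Two limits on the gap.** Protocol 5.6 also says that "subjects who prematurely discontinue study drug treatment should continue to be followed for all regularly scheduled visits". The exception is withdrawal of consent, "in which no further study procedures or study activities can be performed".

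**The concern.** For a subject who leaves the study early, the day-84 visit or call is the only scheduled contact late in the post-dose window. Protocol 5.6 makes that contact optional, while Protocol 6.1 and the SAP treat the window as fully covered. Two things follow if the contact does not take place.

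- **Numerator.** A new infection, cytopenia or hepatic event after the PD visit is captured only if someone reports it unprompted. The chemistry and hematology scheduled for the 84-day visit are lost as well.
- **Denominator.** The unobserved days still count as exposure, so the rate per 100 patient-years is too low.

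The reasons for leaving listed in Protocol 5.5 include AEs, abnormal laboratory results and a wish to stop after the Week 52 visit. The situation is therefore foreseeable. In a study of about 40 subjects, one subject whose only event is missed changes an incidence by 1/40 = 2.5 percentage points.

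**Working it through.** The plan gives no figure of its own to reproduce, so this is person-time arithmetic.

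**Inputs from the documents**
- Credited days = (last dose − first dose) + 84 (SAP 9.1).
- Last dose is at Week 10 (day offset 70) for Week 12 non-responders and at Week 102 (offset 714) for completers (Protocol 4.1).
- The PD visit is preferably within 2 weeks (Protocol 5.6).
- The planned size is up to approximately 40 (Protocol 7.3).

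**Assumptions, not in the documents**
- An early leaver has the last dose at Week 4 (offset 28), is last seen 14 to 28 days later, and has no AE captured after that.
- There are 4, 8 or 12 such leavers in 40, with 20 Week 12 non-responders and the rest completing. The last two groups have their 84-day contact.

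**One leaver**
- Credited: 28 + 84 = 112 days.
- Observed: 28 + 14 = 42, or 28 + 28 = 56 days.
- Ratio: 112/42 = 2.67, or 112/56 = 2.0.

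The ratio depends on when the subject stops. With last contact 14 days after the last dose it is 84/14 = 6.0 for a last dose at Week 0, 154/84 = 1.83 at Week 10 and 434/364 = 1.19 at Week 50. The unobserved time is 70 days in each case.

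**Whole cohort**
A non-responder contributes 70 + 84 = 154 days and a completer 714 + 84 = 798. Each leaver is credited with 112 − 42 = 70, or 112 − 56 = 56, unobserved days.

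| Leavers | Completers | Credited days (years) | Observed days (years) | Credited/observed |
|---|---|---|---|---|
| 4 | 16 | 448 + 3,080 + 12,768 = 16,296 (44.6) | 16,016 to 16,072 (43.8 to 44.0) | 1.017 to 1.014 |
| 8 | 12 | 896 + 3,080 + 9,576 = 13,552 (37.1) | 12,992 to 13,104 (35.6 to 35.9) | 1.043 to 1.034 |
| 12 | 8 | 1,344 + 3,080 + 6,384 = 10,808 (29.6) | 9,968 to 10,136 (27.3 to 27.8) | 1.084 to 1.066 |

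Person-time is overstated by 1.4% to 8.4%. The rate is lowered by 224/16,296 = 1.4% to 840/10,808 = 7.8%.

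The result is sensitive to the number of completers. With 12 leavers, 28 non-responders and no completers, credited time is 1,344 + 4,312 = 5,656 days and the rate falls by 840/5,656 = 14.9%.

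For a subject with the 84-day contact, or one who stays on scheduled visits through day 84, the discrepancy from this source is zero.

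**The case against.** The strongest reply is that Protocol 5.6 opens by keeping drug discontinuers on all scheduled visits, and AEs are assessed at each of them. A subject who stops drug for an AE and stays in the study is therefore asked about AEs throughout the window. This stands, and it removes that group from the concern.

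Other safeguards also stand. Consent withdrawers cannot be followed under any wording. Spontaneous reports are collected to day 84. Known AEs are followed to a satisfactory conclusion (Protocol 6.1) and clinically significant laboratory abnormalities to resolution (Protocol 6.2). Chemistry and hematology are drawn at the PD visit. Against that, the loss-to-follow-up steps in Protocol 5.5 seek the subject's final status and do not set an AE contact at day 84.

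It may also be said that any subject can refuse any visit. That is true, but Protocol 4.1 does not write its contact as optional, and a subject who would not travel but would take a call has no such contact offered in 5.6.

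A reader might infer that late AEs in all early leavers will go unrecorded, or that the subjects most likely to have drug toxicity are the ones missed. The documents support neither. The firm wording in 6.1 and the schedule still applies, and Protocol 5.5 lists many reasons for leaving without any breakdown.

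**Conclusion.** The point holds in a limited form. Protocol 5.6 is inconsistent with 4.1, 6.1, Operations Manual 4.1 and Appendix D on whether early leavers are to have the 84-day contact. SAP 9.1 counts the 84 days whether or not they were observed. The affected group is subjects who leave the study early, have not withdrawn consent and have no day-84 contact. In them, new AEs may be missed unless reported spontaneously.

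The study-level effect on the exposure-adjusted rate is modest, at about 1 to 8% of person-time under the stated assumptions. The 2.0- to 2.7-fold figure describes one hypothetical subject and should not be read as the study-level bias. AE percentages do not use this denominator, so they are lowered only through missed events. The arithmetic does not size that loss.

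**What to change.** 1. **Protocol 5.6.** Reconcile it with 4.1, 6.1 and Appendix D. Every early leaver who has not withdrawn consent is to have the 84-day AE contact by visit, or by call if a visit is not possible. The subject may still refuse; record any refusal and the date of last contact.
2. **SAP 9.1.** End each subject's exposure at the earliest of last dose + 84 days, last contact and data cut-off. The protocol edit alone does not correct the rate, because anyone who refuses or is lost would still be credited with 84 days. The cut-off limit also brings the denominator into line with the window in SAP 9.2.1.

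The cost is a short rewording in each document, a call or visit for a few subjects, and a slightly smaller denominator. The contact is already in the schedule and a call is already permitted there.

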## 5.7 Study Drug

---

Information about the study drug used in this study is presented in [Table 1](#).

**Table 1. Description of Study Drug**

	Investigational Product	Investigational Product Placebo
Investigational product name	Ravagalisimab (ABBV-323)	Placebo
Active ingredient	Ravagalisimab (ABBV-323)	N/A
Dosage Form	Lyophilized powder for solution for injection/infusion in vials	Lyophilized powder for solution for injection/infusion in vials
Strength	100 mg/mL, when reconstituted	N/A, when reconstituted
Frequency of administration	Induction: IV × 1 dose then SC eow Maintenance: SC eow	Induction period only: for IV line flush only

IV = intravenous; eow = every other week; N/A = not applicable; SC = subcutaneous

The study drugs will be supplied in cartons containing one vial with quantities sufficient to accommodate study design. Each vial contains 100 mg ravagalisimab lyophilized powder for solution for injection/infusion, or placebo. Each carton and vial label will contain a unique kit number. This kit number is assigned to a subject via interactive response technology (IRT) and encodes the appropriate study drug to be administered at the subject's corresponding study visit. Each carton and vial will be labeled as required per country requirements. The labels must remain affixed to the cartons and vials. All blank spaces should be completed by site staff prior to dispensing to subject. Study drug will only be used for the conduct of this study.

AbbVie will provide instructions for drug preparation.

## 5.8 Randomization/Drug Assignment

---

All subjects will be assigned a unique identification number by the IRT at the screening visit. For subjects who rescreen, the screening number assigned by the IRT at the initial screening visit should be used. No randomization will be used in the single arm, open-label study.

## 5.9 Protocol Deviations

---

The investigator is responsible for complying with all protocol requirements, written instructions, and applicable laws regarding protocol deviations. Protocol deviations are prohibited except when necessary to eliminate an immediate hazard to study subjects. If a protocol deviation occurs (or is identified, including those that may be due to cases of state of emergency or pandemic situations), the investigator is responsible for notifying independent ethics committee (IEC)/independent review board (IRB), regulatory authorities (as applicable), and AbbVie.

# 6 SAFETY CONSIDERATIONS

## 6.1 Complaints and Adverse Events

---

### Complaints

A complaint is any written, electronic, or oral communication that alleges deficiencies related to the physical characteristics, identity, quality, purity, potency, durability, reliability, safety, effectiveness, or performance of a product/device. Complaints associated with any component of this investigational product must be reported to AbbVie.

#### Product Complaint

A product complaint is any complaint related to the biologic or drug component of the product or to the medical device component(s).

For a product this may include, but is not limited to, damaged/broken product or packaging, product appearance whose color/markings do not match the labeling, labeling discrepancies/inadequacies in the labeling/instructions (e.g., printing illegible), missing components/product, device not working properly, or packaging issues.

Product complaints concerning the investigational product and/or device must be reported to AbbVie within 1 business day of the study site's knowledge of the event. Product complaints occurring during the study will be followed up to a satisfactory conclusion.

#### Medical Complaints/Adverse Events and Serious Adverse Events

An adverse event is defined as any untoward medical occurrence in a subject or clinical investigation subject administered a pharmaceutical product and which does not necessarily have a causal relationship with this treatment. An adverse event can therefore be any unfavorable and unintended sign (including an abnormal laboratory finding), symptom, or disease temporally associated with the use

of a medicinal (investigational) product, whether or not the event is considered causally related to the use of the product.

The investigators will monitor each subject for clinical and laboratory evidence of adverse events on a routine basis throughout the study. All adverse events will be followed to a satisfactory conclusion.

An elective surgery/procedure scheduled to occur during a study will not be considered an adverse event if the surgery/procedure is being performed for a pre-existing condition and the surgery/procedure has been pre planned prior to study entry. However, if the pre-existing condition deteriorates unexpectedly during the study (e.g., surgery performed earlier than planned), then the deterioration of the condition for which the elective surgery/procedure is being done will be considered an adverse event.

If an adverse event, whether associated with study drug or not, meets any of the following criteria, it is to be reported to AbbVie clinical pharmacovigilance or CRO (as appropriate) as a serious adverse event within 24 hours of the site being made aware of the serious adverse event (refer to Section 4.3 of the Operations Manual [[Appendix F](#)] for reporting details and contact information):

Death of Subject	An event that results in the death of a subject.
Life-Threatening	An event that, in the opinion of the investigator, would have resulted in immediate fatality if medical intervention had not been taken. This does not include an event that would have been fatal if it had occurred in a more severe form.
Hospitalization or Prolongation of Hospitalization	An event that results in an admission to the hospital for any length of time or prolongs the subject's hospital stay. This does not include an emergency room visit or admission to an outpatient facility.
Congenital Anomaly	An anomaly detected at or after birth, or any anomaly that results in fetal loss.
Persistent or Significant Disability/Incapacity	An event that results in a condition that substantially interferes with the activities of daily living of a study subject. Disability is not intended to include experiences of relatively minor medical significance such as headache, nausea, vomiting, diarrhea, influenza, and accidental trauma (e.g., sprained ankle).

**Important Medical Event  
Requiring Medical or Surgical  
Intervention to Prevent  
Serious Outcome**

An important medical event that may not be immediately life-threatening or result in death or hospitalization, but based on medical judgment may jeopardize the subject and may require medical or surgical intervention to prevent any of the outcomes listed above (i.e., death of subject, life threatening, hospitalization, prolongation of hospitalization, congenital anomaly, or persistent or significant disability/incapacity). Additionally, any elective or spontaneous abortion or stillbirth is considered an important medical event. Examples of such events include allergic bronchospasm requiring intensive treatment in an emergency room or at home, blood dyscrasias or convulsions that do not result in inpatient hospitalization, or the development of drug dependency or drug abuse.

All adverse events reported from the time of study drug administration until 84 days after discontinuation of study drug administration will be collected, whether solicited or spontaneously reported by the subject. In addition, serious adverse events and protocol-related nonserious adverse events will be collected from the time the subject signs the study-specific informed consent.

AbbVie will be responsible for Suspected Unexpected Serious Adverse Reactions (SUSAR) reporting for the Investigational Medicinal Product (IMP) in accordance with global and local requirements.

Adverse events will be monitored throughout the study to identify any of special interest that may indicate a trend or risk to subjects.

